1. PURPOSE OF THE STUDY

a. Brief Summary

The current study seeks to evaluate an evidence-based family intervention for teens with type 1 diabetes and their parents to offset the psychosocial and diabetes self-management risks during this period. This study will collect survey and biomedical data to assess this program in a randomized controlled trial. 165 families (including an adolescent and parent) will be enrolled, complete surveys, provide biomedical data via glucose monitors and receive the intervention. The results of this study will inform future intervention redesign to provide more judicious interventions to be disseminated across diabetes care.

b. Objectives

This study will evaluate the relative efficacy of each of the individual intervention components and also identify the mechanisms of actions (mediators) that are most impacted by these types of interventions as well as most linked to long-term outcomes for adolescents. This information will provide a more in-depth understanding of family-based program efficacy for teens with adolescents and provide more judicious and streamlined intervention options to be offered in diabetes clinics in the future.

c. Rationale for Research in Humans

In order to optimize family-based interventions, we need to evaluate adolescent and parent outcomes.

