2. STUDY PROCEDURES

a. Procedures

Recruitment and enrollment: Informed parental consent and adolescent assent (for ages 12-17) or consent (for ages 18-19) will be secured prior to enrollment. The recruitment phase will span 3 years. Participants will be recruited based on A1C results in charts or shared reports that fall within 4 weeks of baseline data collection.

Randomization and assignment: After enrollment, each family will be randomly assigned to either the intervention condition (50%) or the waitlisted control condition (50%), regardless of all other characteristics or variables. Once randomized, instructions for scheduling and accessing the

intervention will be immediately provided to the intervention group. The intervention group will also be offered to participate in a voluntary monthly parent group with other parent participants to discuss the intervention. The waitlisted control group will receive the intervention after 6-month follow-up.

Intervention: The intervention will be conducted by the PI or an interventionist (clinically trained research staff) via Zoom, an easy to use, accessible, and HIPAA- compliant software. Participants and facilitators can interact and screen- share to simultaneously view materials and videos of each other.

Data collection: Data collection: Online surveys (adolescent and parent report on demographics, parent-adolescent relationship, diabetes, and family issues) and glucose monitoring data will be captured at baseline and 3-month (proximal endpoint), 6-month (primary endpoint), and 12-month (distal endpoint) follow-ups.

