Glucose monitoring data will be collected via glucose monitors that are already in use, among participants already using these devices at the time of enrollment, with data being shared by the participant with the research team via secure online portals created and run by their corresponding device company. For participants who are not already using glucose monitors at the time of enrollment, Libre 2 glucose monitor devices will be provided by study staff, as well as training on use following FDA-approved self-start guides that are available online. Research staff will also provide support throughout use, and will be used to collect 2 weeks of data at each time point. A smaller set of surveys will also be conducted at approximately 2-, 4-, and 6-week follow-ups (after every 2 sessions for the intervention group and at corresponding time points for the control group). Participants will be asked to report their A1Cs (or gathered from medical records) at baseline and 6-month and 12-month follow-ups. If participants do not have an A1c result from the target period, they will be sent via mail a blood collection kit that can be completed at home and returned via mail to a laboratory where the specimen will be tested for HbA1c.

b. Procedure Risks

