The procedures and treatment offered by this study are additive the current services and no alternative are currently available.

f. Will it be possible to continue the more (most) appropriate therapy for the participant(s) after the conclusion of the study?

Therapy options (in the form of behavioral or psychosocial interventions) will be offered to participants at the conclusion of the study, if indicated, including referrals to both in-clinic and external services.

g. Study Endpoint(s)

3-month (proximal endpoint), 6-month (primary endpoint), and 12-month (distal endpoint) follow-ups. Endpoints were selected based on prior evaluations of similar interventions for youth with T1D showed effects at 6-month follow-up and maintained thereafter. Given the wait-listed control group design, we will be able to test pre-post differences as well as group differences to evaluate efficacy.

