We will enroll 330 participants (165 adolescents with type 1 diabetes and their 165 caregivers). Participants will be asked to participate in a 6-session family-based intervention delivered via the internet, complete online surveys, provide glucose monitoring data either via continuous glucose monitors (CGMs) that the have already been using prior to enrollment or blinded CGMs provided by the study, and provide A1C test results that will be collected via chart review or from participants sharing their test results at baseline, 6-month, and 12-month follow-up. We will compensate each parent and each adolescent participant with a total of \$\frac{1}{2}\$ worth of gift cards for complete data collection. Graduated incentives are provided at each time point:

\square Baseline = \$
\Box First intermediate survey = \$
\square Second intermediate survey = \$
\Box Third intermediate survey = \$
\square 3-month follow-up = \$
\Box 6-month follow-up = \$
□ 12-month follow-up = \$

l. Costs to Participants

None.

m. Planned Duration of the Study

The probable duration of the entire study is 4.5 years. We anticipate screening will require 5 minutes, recruitment of all 165 participants can take up to 3 years, and activate participation in the study will require approximately 12 months. Each participant will spend 8 hours total on study participation and analysis of participant data will require approximately 1 year. Surveys will require approximately 30 minutes each to complete and each intervention sessions for the intervention group will require approximately 10-20 minutes each.

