Insul-In This Together Program: Optimizing Family-based Interventions for Adolescents With Type 1 Diabetes and Their Parents

Statistical Analysis Plan

NCT04589689

[figure not shown]
May 11, 2021

Statistical Analysis Plan

[figure not shown]
1. Planned sample size was 150 enrolled parent-adolescent dyads. The final sample included 157 parent-adolescent dyads.
2. Basic two-sided t-tests for primary and secondary outcomes using a p-value cutoff of <.05. Compared participants based on condition assignments: intervention versus waitlisted control.
3. Simple regression models: test main effects on outcomes at 3-month and 6-month follow-ups (in Mplus)
 - a. Covariates: Teen age, diabetes duration, baseline TIR, baseline QOL, and baseline outcome (if other than TIR or QOL)
 - b. Auxiliary variables (to inform data imputation, but not directly included in model): Teen gender, baseline A1c, Teen PAID, and Parent PAID
4. Moderation analyses: separate regression models for each outcome that include set of covariates and an interaction term of condition x moderator.
 - a. Covariates: age, diabetes duration, baseline QOL, and baseline TIR
 - b. Outcomes: QOL, TIR, A1c, Teen PAID, and Parent Paid
 - c. Moderators (at baseline):
 1. Closed loop
 2. A1c \leq 7.5%
 3. TIR \geq 70%
 4. Race/ethnicity
 5. Income
 6. Insurance
 7. Baseline level of corresponding outcome
5. Mediation analyses: single mediator models
 - a. Mediator: immediate posttest
 - b. Outcomes: 3-month and 6-month follow-ups
6. 12-month follow-up – combine both conditions and look through 6-months (but for control the 6-month value 12-month value)

Regression Model

6-Month Follow-Up

Moderation Models

Single Mediator Model

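### Protocol 1.b promises the relative efficacy of each component, but the package-versus-waitlist design identifies only the whole-program effect on the 3- and 6-month outcomes

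*Protocol*

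**What the plan says.** Protocol 1.b (Objectives) sets two aims. The first is about components: "This study will evaluate the relative efficacy of each of the individual intervention components". The second is about mechanisms: to "identify the mechanisms of actions (mediators) that are most impacted by these types of interventions as well as most linked to long-term outcomes". The same section expects the results to lead to leaner intervention options for diabetes clinics.

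The design is in Protocol 2.a (Procedures). Families are allocated in equal proportions to intervention or waitlist, and the waitlisted families receive the intervention after the 6-month follow-up. Protocol 4.k describes what is delivered: "Participants will be asked to participate in a 6-session family-based intervention delivered via the internet". One further element exists in the intervention arm only: "The intervention group will also be offered to participate in a voluntary monthly parent group with other parent participants". Short surveys are planned at about 2, 4 and 6 weeks, that is, "after every 2 sessions for the intervention group and at corresponding time points for the control group". On efficacy, Protocol 2.g says "we will be able to test pre-post differences as well as group differences to evaluate efficacy".

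In the SAP, item 2 compares the two conditions, item 3 tests main effects at 3 and 6 months, and item 4 adds condition-by-moderator interactions. Item 5 fits one mediator per model, measured at immediate posttest, with outcomes at 3 and 6 months. Item 6 pools the conditions for the 12-month analysis. No item in the readable text contains a component term.

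**The concern.** To compare the efficacy of components, something must vary which components a family receives. Nothing in the protocol does so. Every intervention family is offered the same six sessions and the same parent group, and every waitlist family is offered neither before month 6. Attendance at the parent group is by choice, so attenders and non-attenders are not randomised groups.

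What is at stake is the use to which Protocol 1.b puts the answer. Streamlining a program means choosing which parts to retain. A statement from this trial that one part works better than another would rest on a comparison that the trial does not make.

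A smaller, related point concerns the second aim. Models fitted one mediator at a time can show that a mediator moves with the intervention and is associated with the outcome. They do not separate mediators that are correlated with each other, so their results need to be described accordingly.

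**Working it through.** The documents state no figure for component efficacy, so there is none to reproduce. The main check is one of identification.

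**1. What the two arms can estimate on the 3- and 6-month outcomes.** The documents do not list the components. As an assumption, take the blocks between short surveys: 6 sessions / 2 = 3 blocks. The parameters are an intercept and three block effects, 4 in all.

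- Waitlist row: (1, 0, 0, 0)
- Intervention row: (1, 1, 1, 1)

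The rank is 2 for 4 parameters. Only the intercept and the sum of the three block effects are estimable. Adding the offer of the parent group makes the rows (1, 0, 0, 0, 0) and (1, 1, 1, 1, 1), with rank 2 for 5 parameters. For contrast, a full 2 x 2 x 2 factorial has rank 4 for the 4 parameters. Rank does not depend on the number of families, so more enrolment would not help. Component contrasts identified by randomisation on these outcomes: 0.

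**2. The other comparisons the documents name.** A pre-post difference in either arm is again a difference before and after the whole package. The pooled 12-month analysis in SAP item 6 uses waitlist families who have crossed over to the same package. Neither adds a component contrast.

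**3. What the short surveys add.** Because controls are surveyed at matching times, the arm differences at weeks 2, 4 and 6 are randomised effects of sessions 1-2, 1-4 and 1-6. Only the first is a single block. No variation in session order is described, so later blocks are confounded with order and with what came before.

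Precision, taking the 157 dyads of SAP item 1 split 78/79, unadjusted and without attrition, in SD of a measure that the readable text does not name:

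- 2-week contrast, 95% half-width: t(155) x sqrt(1/78 + 1/79) = 0.315 SD.
- Sessions 3-4 minus sessions 1-2, if effects are additive and not delayed: (D4 - D2) - D2 = D4 - 2 x D2, where D2 and D4 are the arm differences at weeks 2 and 4. The variance factor is 1 + 4 - 4 x rho = 5 - 4 x rho, so the half-width is 0.315 x sqrt(5 - 4 x rho). At assumed between-wave correlations of 0.3 / 0.5 / 0.7 this is 0.615 / 0.546 / 0.468 SD.

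**4. Single-mediator models.** Suppose the arm shifts two mediators by a, only the first affects the outcome (path b), their within-arm correlation is r, and residual SDs are 1. In its own model the inert mediator's path estimates b x r, so its apparent indirect effect is a x b x r. With assumed a = 0.5 and b = 0.4 this is 0.5 x 0.4 x r = 0.06 / 0.10 / 0.14 at r = 0.3 / 0.5 / 0.7, against 0.5 x 0.4 = 0.20 for the active one. With a = 0.3 and b = 0.2 it is 0.018 / 0.030 / 0.042. At r = 0 it is zero. The documents give none of these inputs. The calculation shows only that correlated mediators are not separated.

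**The case against.** **The short surveys do carry component information.** This stands in part. The 2-week wave gives a randomised contrast of sessions 1-2 against none. It would be wrong to say that the trial has no component-level information of any kind. But these contrasts are on a smaller survey set, the later ones are cumulative, and the readable SAP names no analysis of them by block. They do not reach the 3- and 6-month outcomes.

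**The mediator plan is adequate for what is asked.** This largely stands. A reader might infer that item 5 will produce false mechanisms or a wrong ranking and must be replaced. The documents do not support that. Protocol 1.b asks which mediators are most affected and most strongly linked, and neither it nor SAP item 5 claims an independent link. Simulation with 157 families and the assumed paths above gives rates that depend wholly on those assumptions. An inert mediator is declared significant in 4 / 24 / 57 / 80% of trials at r = 0 / 0.3 / 0.5 / 0.7 with a = 0.5 and b = 0.4, but in 3 / 5 / 11 / 18% with a = 0.3 and b = 0.2. Baseline adjustment, left out of the simulation, could lower r.

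Ranking by the mediator-to-outcome path hardly differs between single and parallel models: the wrong mediator comes first in 0.8 v 0.7% at r = 0.5 with the stronger paths. Ranking by indirect effect differs more, 14.7 v 3.6% at r = 0.7, again under assumed values.

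**A parallel-mediator model has its own cost.** This stands. With two mediators at r = 0.7 the standard error of the active path rises from 0.081 to 0.113. With six equally correlated mediators it is about 0.14, and at a = 0.5 and b = 0.2 detection falls from about 61% in the single model to 37% with two mediators and about 27% with six. In a chain (arm to first mediator 0.5, first to second 0.5, second to outcome 0.4) the first mediator's real indirect effect of 0.5 x 0.5 x 0.4 = 0.10 is estimated as 0.00.

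**Changing an objective after enrolment may hide what was promised.** This stands, and the remedy must keep the present wording visible.

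**Conclusion.** The component clause of Protocol 1.b cannot be met as written. On the 3- and 6-month outcomes the trial identifies the effect of the whole program (six sessions plus the offer of the parent group) against waitlist, and no component contrast at any sample size. This follows from the allocation alone. The three-block split is only an illustration: any division of one package given to one arm leaves rank 2. That the SAP has no component analysis is a statement about its readable text, since its model diagrams are not shown.

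Two stronger conclusions do not follow. The randomised comparison of program with waitlist up to 6 months is not called into question by this point. Nor is the mediator analysis shown to be wrong: the one general statement that holds is that single-mediator models do not separate correlated mediators, and the size of that effect here is unknown, because the documents give no mediator names, number, paths or correlations.

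This should be corrected, because it governs what the report may say about streamlining the program.

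**What to change.** - Restate the component clause of Protocol 1.b as efficacy of the whole program versus waitlist. Date the change, keep the present wording visible beside it, and label it as made after enrolment. The SAP already reports that "The final sample included 157 parent-adolescent dyads", so it cannot be presented as prospective.
- State in the SAP and the report that relative component efficacy on the 3- and 6-month outcomes cannot be assessed, and draw no conclusion from this trial about which components to keep or drop.
- Keep the mediator objective and the single-mediator models. Describe their results as one-at-a-time associations that do not separate correlated mediators.
- Optional and exploratory, also labelled post-enrolment: an arm-by-wave description of the short surveys, with the 2-week wave reported as sessions 1-2 versus none and the later waves as cumulative and order-confounded; and a parallel-mediator sensitivity model reported beside the single-mediator models with its assumptions.

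The required changes are wording only, at the price of a narrower objective. The options need no new data collection if the planned surveys were completed, which the SAP does not report. The parallel model loses precision as mediators are added, and their number is not stated, so it should not be the sole basis for comparing mediators.

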2. STUDY PROCEDURES

a. Procedures

Recruitment and enrollment: Informed parental consent and adolescent assent (for ages 12-17) or consent (for ages 18-19) will be secured prior to enrollment. The recruitment phase will span 3 years. Participants will be recruited based on A1C results in charts or shared reports that fall within 4 weeks of baseline data collection.

Randomization and assignment: After enrollment, each family will be randomly assigned to either the intervention condition (50%) or the waitlisted control condition (50%), regardless of all other characteristics or variables. Once randomized, instructions for scheduling and accessing the

intervention will be immediately provided to the intervention group. The intervention group will also be offered to participate in a voluntary monthly parent group with other parent participants to discuss the intervention. The waitlisted control group will receive the intervention after 6-month follow-up.

Intervention: The intervention will be conducted by the PI or an interventionist (clinically trained research staff) via Zoom, an easy to use, accessible, and HIPAA- compliant software. Participants and facilitators can interact and screen- share to simultaneously view materials and videos of each other.

Data collection: Data collection: Online surveys (adolescent and parent report on demographics, parent-adolescent relationship, diabetes, and family issues) and glucose monitoring data will be captured at baseline and 3-month (proximal endpoint), 6-month (primary endpoint), and 12-month (distal endpoint) follow-ups.

Glucose monitoring data will be collected via glucose monitors that are already in use, among participants already using these devices at the time of enrollment, with data being shared by the participant with the research team via secure online portals created and run by their corresponding device company. For participants who are not already using glucose monitors at the time of enrollment, Libre 2 glucose monitor devices will be provided by study staff, as well as training on use following FDA-approved self-start guides that are available online. Research staff will also provide support throughout use, and will be used to collect 2 weeks of data at each time point. A smaller set of surveys will also be conducted at approximately 2-, 4-, and 6-week follow-ups (after every 2 sessions for the intervention group and at corresponding time points for the control group). Participants will be asked to report their A1Cs (or gathered from medical records) at baseline and 6-month and 12-month follow-ups. If participants do not have an A1c result from the target period, they will be sent via mail a blood collection kit that can be completed at home and returned via mail to a laboratory where the specimen will be tested for HbA1c.

b. Procedure Risks

The above procedures present minimal risk. Engaging in the intervention modules carries minimal risk for emotional discomfort or stress. Subjects will have the option of not participating in conversations or exercises in the intervention modules that cause them any discomfort. They will also be free to withdraw from participating in the intervention and/or overall study at any time. All intervention modules will be carried out by [name], a licensed clinical psychologist (license #29814) or a clinically trained interventionist who will be consistently supervised by [name]. Survey measures are non-invasive and present minimal risk. Glucose monitors are minimally invasive and provide no added level of risk or discomfort beyond routine diabetes management tasks. A1C home test kits present minimal risk as long as participants practice safe hygiene practices and follow the instructions provided. Finger lancing is part of the usual care for people with diabetes and should not be a significant contributor to risks in this study. A small drop of blood will be obtained by finger stick to measure blood glucose and HbA1c. This is a standard method to obtain blood for routine hospital laboratory tests. Pain is common at the time of lancing. In about 1 in 10 cases, a small amount of bleeding under the skin will produce a bruise. A small scar may persist for several weeks. The risk of local infection is less than 1 in 1000. Nevertheless, our staff (including [name] who has extensive experience with diabetes devices) will be available to address any potential discomfort or adverse responses to these procedures that might arise and will connect families with additional mental health or medical services if needed. Adolescent and caregiver participants will be advised of their rights to withdraw from the intervention at any time without penalty or consequence on their receipt of future health care services at Stanford University's Lucile Packard Children's Hospital or affiliated clinics.

c. Use of Deception in the Study

No deception will be used.

5/11/21 Page 2 of 11

d. Use of Audio and Video Recordings

Video recordings of intervention sessions led by interventionists will be collected for clinical supervision and quality assurance purposes. These recordings will be destroyed once no longer needed for clinical supervision/ongoing training purposes. All recordings will be destroyed before the study ends.

e. Alternative Procedures or Courses of Treatment

The procedures and treatment offered by this study are additive the current services and no alternative are currently available.

f. Will it be possible to continue the more (most) appropriate therapy for the participant(s) after the conclusion of the study?

Therapy options (in the form of behavioral or psychosocial interventions) will be offered to participants at the conclusion of the study, if indicated, including referrals to both in-clinic and external services.

g. Study Endpoint(s)

3-month (proximal endpoint), 6-month (primary endpoint), and 12-month (distal endpoint) follow-ups. Endpoints were selected based on prior evaluations of similar interventions for youth with T1D showed effects at 6-month follow-up and maintained thereafter. Given the wait-listed control group design, we will be able to test pre-post differences as well as group differences to evaluate efficacy.

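### Baseline device class is missing from the TIR and A1c main-effect models, and assignment is not stratified by it: a small loss of precision, not a bias

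*Protocol*

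**What the plan says.** Protocol section 2.a assigns families 1:1, the control half going to "the waitlisted control condition (50%), regardless of all other characteristics or variables". No baseline factor enters the assignment. The text does not say whether blocks were used.

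The same section gives two sources of glucose data. For current users, "Glucose monitoring data will be collected via glucose monitors that are already in use". For everyone else, "Libre 2 glucose monitor devices will be provided by study staff". The section on payments (4.k) describes the supplied devices as "blinded CGMs provided by the study".

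The SAP treats device use as relevant in one place only: closed loop heads the list of baseline moderators in item 4c, where the models "include set of covariates and an interaction term of condition x moderator".

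The main-effect regression in item 3a has "Covariates: Teen age, diabetes duration, baseline TIR, baseline QOL, and baseline outcome (if other than TIR or QOL". The auxiliary variables in item 3b, used for imputation only, are "Teen gender, baseline A1c, Teen PAID, and Parent PAID". Neither list contains device class. Item 2 plans "Basic two-sided t-tests for primary and secondary outcomes using a p-value cutoff of <.05", with no covariates.

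**The concern.** Device class plausibly affects TIR in two ways. An automated system changes the glucose profile itself, and the sensor and its display (own monitor, or a blinded study sensor) may change what is recorded. The trial will hold this variable at baseline: monitor use at enrolment decides who is given a study sensor, and closed-loop status is needed for item 4.

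With assignment unstratified, the arms can differ in device mix by chance. Where the analysis does not adjust for device class, two things follow. Given the split that actually occurred, part of the device difference sits in the treatment contrast. And the device-related share of outcome variance stays in the error term. At stake is the precision of the TIR contrast, and how far a reader can set aside device mix as an explanation of it. A1c shares the first route only, because it comes from charts, participant reports or a mailed kit and not from the glucose sensor.

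**Working it through.** The documents give no power, effect size, SD, dropout or device mix, so there is no stated figure to reproduce. Only N = 157 (SAP item 1) is theirs. The other inputs are assumptions: share p of the device class 20% to 40%; within-class TIR SD s = 15 points; class gap D = 5 to 15 TIR points; within-class correlation r between baseline and follow-up 0.5 to 0.8. Steps 1 to 5 treat device class as two groups with n = 157/2 = 78.5 per arm and no missing data. The results are for TIR; nothing was calculated for A1c.

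**1. Chance imbalance.** The SD of the between-arm difference in share is √(p(1−p)·2/n).
- p = 0.2: √(0.16 × 2/78.5) = 6.4 points; 95% range ±12.5; chance of a difference of 10 points or more, 12%.
- p = 0.4: √(0.24 × 2/78.5) = 7.8 points; 95% range ±15.3; chance of 10 points or more, 20%.

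**2. Stable gap.** Let v = p(1−p).
- Variance at each visit: s² + vD².
- Covariance between visits: rs² + vD².
- Slope on baseline TIR: b = covariance/variance.
- Residual variance given baseline TIR: variance − b × covariance.
- Residual variance given baseline TIR and device class: s²(1−r²).
- SE: √(2 × residual variance/n).
- An imbalance i shifts the t-test contrast by iD and the baseline-adjusted contrast by iD(1−b).

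Example with p = 0.4, D = 10, r = 0.7: variance 225 + 24 = 249; covariance 157.5 + 24 = 181.5; b = 0.73. The residual variance is 249 − 132.3 = 116.7 with baseline TIR, and 225 × 0.51 = 114.75 with device class added. That is 1.7% less, an SE ratio of 1.008.

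With p = 0.4, D = 10 and the imbalance at its 95% limit (15.3 points), in TIR points:

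| r | b | Shift, t-test | Shift, baseline TIR in model | SE, t-test | SE, baseline TIR | SE, baseline TIR + device |
|---|---|---|---|---|---|---|
| 0.5 | 0.55 | 1.53 | 0.69 | 2.52 | 2.11 | 2.07 |
| 0.7 | 0.73 | 1.53 | 0.42 | 2.52 | 1.72 | 1.71 |
| 0.8 | 0.82 | 1.53 | 0.28 | 2.52 | 1.44 | 1.44 |

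Baseline TIR thus removes 55% to 82% of the shift here. Over all the assumed values, adding device class removes 0.2% to 6.1% of the residual variance, and the SE ratio runs from 1.001 to 1.032.

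**3. Gap that widens by g after baseline** (D = 10, p = 0.2 or 0.4, r = 0.5 or 0.7). The follow-up variance becomes s² + v(D+g)² and the covariance rs² + vD(D+g). The SE ratio, without against with device class, is 1.04 to 1.06 for g = 5 and 1.10 to 1.15 for g = 10. At p = 0.4, r = 0.7 and the 95% imbalance limit, the shift left after baseline adjustment is 1.11 points (SE 1.81) for g = 5 and 1.80 points (SE 1.96) for g = 10.

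**4. Unadjusted t-test.** With a stable gap, device class explains 1.7% to 19.4% of the raw variance. Leaving it in the error term makes the SE larger by a factor of 1/√(1−0.017) = 1.009 to 1/√(1−0.194) = 1.114.

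**5. Cost of the extra terms.** Two added coefficients cost roughly 2/157 = 1.3% of variance, or 0.6% of the SE. The ratios in steps 2 and 3 leave this out, so at the bottom of the stable range the net gain is nil or slightly negative.

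**6. Simulation.** 10,000 trials per scenario, N = 157, three classes of 40/50/10% with stable gaps of +10/0/−8 points. The fitted models pay the cost in step 5.

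| Model | Type I error, r = 0.5 / 0.7 | Power for 5 points, r = 0.5 / 0.7 |
|---|---|---|
| t-test | 4.6% / 5.1% | 49.1% / 48.5% |
| Baseline TIR | 4.5% / 4.8% | 64.6% / 81.4% |
| Baseline TIR + device | 4.6% / 5.0% | 66.2% / 81.6% |

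**The case against.** The strongest reply is that item 3a has already done most of the work. A stable device difference is largely carried by baseline TIR, and the A1c model also holds baseline A1c. What is left is worth 0.2 to 1.6 points of power in the simulation. Every input except N is assumed, and closed loop is examined in item 4. Nearly all of this stands, and it is why the point is minor. Item 4 does not close the gap, however: it tests effect modification and does not adjust the main effect, and the SAP does not say whether the moderator's own term is in that model.

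Four stronger readings are tempting but not supported.

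- **That omitting device class biases the result.** Chance imbalance under randomisation is random error already reflected in the SE. Simulated type I error stays between 4.5% and 5.1%. The shifts above are conditional on an uneven split.
- **That the Protocol specifies simple randomisation without blocks.** It rules out characteristics as assignment factors and is silent on blocking. Unstratified blocks would fit its wording.
- **That the loss is worth some 21 families.** Take SD 16 and r = 0.7, so that residual variance is 256 × 0.51 = 130.6. Let a 40% closed-loop class finish 8 points higher at equal baseline TIR. The share of residual variance is then 0.24 × 64/130.6 = 11.8%, and 157 × (1/(1−0.118) − 1) = 21. But with r read as the within-class correlation, a stable gap would have to be 8/(1−0.7) = 27 points. In effect this figure needs a gap that widens after baseline, and the documents offer no evidence of one.
- **That three device classes are defined in the plan.** The Protocol describes two data sources, and closed loop appears only as a moderator. The three-way split is a reasonable inference.

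**Conclusion.** The point holds as a minor improvement to precision. Device class is in neither the assignment nor the main-effect model, although the trial will have it at baseline and the SAP itself regards closed loop as relevant to TIR and A1c. The treatment comparison remains valid.

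In the item 3 regression the expected gain for TIR is small if device differences are stable, and it becomes material only if they grow after baseline. The documents do not show which applies. The item 2 t-test has no protection against a device imbalance, although most of its lower power in the simulation comes from leaving out baseline TIR, not device class.

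Two limits apply. The documents do not name TIR as the primary outcome; 6 months is the primary time point, and TIR is among the listed outcomes. For A1c the case rests on reasoning alone.

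**What to change.** In SAP item 3a, add baseline device class (closed loop / own monitor without closed loop / study-supplied sensor) to the covariates for the TIR and A1c models. Define it from status at enrolment and not from later device use, which could itself respond to the intervention. If outcome results have already been seen, keep the stated model and report the version with device class as a labelled sensitivity analysis. A line giving device mix by arm would let readers see the actual split.

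The cost is two degrees of freedom, with no new data, visits or families.

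The change does nothing for the item 2 t-tests, so it helps only where the regression carries the conclusion. Which of the two analyses leads is a separate matter for the SAP to settle. No change to the assignment procedure is proposed: the SAP reports a final sample of 157, so stratified blocks can no longer help, and rewriting the Protocol now would misdescribe how families were assigned.
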